a. Recent cardiovascular event. Cardiovascular events (stroke, myocardial infarct, deep vein thrombosis, pulmonary embolus or thrombosis) may interfere with platelet function studies and with various mediators during the first months after the event. Patients who had such an event within the last 6 months will be excluded.

b. Patients with uncontrolled hypertension. This will remove a confounding factor from analysis of the endothelial flow studies and increase safety. 8. Informed consent: Individuals who are unwilling or unable to consent, or in the case of minors who are unwilling or unable to assent will be excluded due to lack of ability to ensure informed consent.

9. Study compliance and integrity: Individual who anticipate an inability to comply with study procedures and requirements will be excluded.

10. Hypertriglyceridemia. Individuals with a triglyceride level above 300 mg/dl will be excluded from the study. An associated increase in triglyceride levels with administration of taurine has been reported (as has a decrease in triglycerides) Exclusion of individuals who have a history of hypertriglyceridemia will decrease the likelihood that a study related increase in serum triglycerides would result in health care risks. This is a conservative approach as acute health care risk is generally seen in the setting of triglycerides > 1000 mg/dl. Historic triglyceride levels (within 5 years of the date of consent) can be used to assess eligibility. This lacking, triglycerides can be obtained as part of the study and assessed prior to administration of taurine.

F. Planned Enrollment: Enter # of Subjects in the Table Below: review the numbers for 12 and women = male (given your statement in 7A inclusion of women)

Ethnic Categories	Gender		
	Females	Males	Total
Hispanic or Latino	2	2	4
Not Hispanic or Latino	8	8	16
Ethnic Categories: Total of All Subjects	10	10	20
Racial Categories			
American Indian/Alaska Native	0	0	0
Asian	1	0	1
Native Hawaiian or Other Pacific Islander	0	0	0
Black or African American	1	2	3
White	8	8	16

Racial Categories: Total of All Subjects*	10	10	20
--	-----------	-----------	-----------

*The "Ethnic Categories Total of All Subjects" **must be equal to** the "Racial Categories Total of All Subjects"

Data listed here **reflects US population demographics and is an estimate..**

G. Study Design Details:

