The PI will monitor data and report on the protocol safety issues. Pregnancy test results which are part of the inclusion criteria will be reviewed the day of specimen collection, prior to 5 PM (and hence prior to start of taurine supplementation). Serum triglyceride level will also be reviewed prior to start of taurine supplementation. Those with levels greater than 300 mg/dl will be excluded from the study. Participants will be encouraged to call regarding any adverse event of concern to them during the period of supplementation. A review of systems, utilizing a form with questions targeted to capture potential adverse effects (See Intake Sheet and Adverse Event/Compliance Sheet, Appendix V – Supplemental Materials) will be administered prior to the first dose and with the last dose of taurine, and again 1 week after completion of the study (the last survey administered by telephone). This questionnaire will be administered by the PI, co-investigator, or CTRC nursing staff. Participants will also be questioned directly about potential adverse effects relative to taurine intake at the time of their last dose. A physical examination including blood pressure will be done prior to taurine administration, and at the completion of the study. Blood samples for complete blood count, comprehensive metabolic panel, and a lipid panel will be obtained prior to taurine administration, and at the completion of the study.

Adverse events and monitoring lab studies data will be reviewed within 5 working days after the subject has completed the study protocol. Compiled data will be examined 1. after the first two patients have been treated at the lower dose of 50 mg/kg/day (3 g/day), 2. after the first four adults have completed the study prior to opening the study for recruitment of children, 3. at the mid-point of the next patient recruitment (after 7 subjects have completed the protocol and after 12 subjects) 4. at the end of the study by the PI, co investigators and data Safety Officers. The data Safety Officers will consist of two clinical geneticists and one alternate clinical geneticists not associated with the study but knowledgeable of the studied condition. The PI and the data Safety Officers board will be looking for repeat

adverse events (AEs) or trends in AEs. In addition, the data Safety Officers and PI and co-investigators will convene within one week of reporting of a SAE.

Current Safety Officers:

[name]
[contact]
Children's Hospital Colorado

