Special Care Clinic
[name]
[name]

[name]
[contact]
[name]

[name] (alternate)
[contact]
[name]

Unanticipated problem or events, especially problems or events that are possibly or probably related to the study or research procedures will also be looked for. This includes monitoring for serious adverse events (SAEs) since such an event is not anticipated. In an event of an SAE, the monitoring PI will discuss the event with one of the co-investigator MDs within 24 hours of knowledge of the event to allow for decisions regarding the data and the safety to all participants. All unanticipated problems and unanticipated events will also be discussed with one of the co-investigating MDs within five working days of knowledge of the problem or event. Any identified trend in AEs will also be discussed within five working days of knowledge of the trend with one of the co-investigator MDs. Of note, the minimal risk for adverse events relative to taurine intake, the low number of participants (N=16 with drug exposure) and short duration of the study (5 days) make it very unlikely that any AE trend would be detected much before the end of the study.

There are no conflicts of interest for the PI or the co-investigator MDs responsible for data safety management.

B. Describe SAEs and AEs for this protocol and the SAE/AE reporting plan:

Events that result in death, immediate hospitalization, or prolonged hospitalization to prevent death or serious disability will be considered SAEs. Any other untoward medical occurrence temporally associated with the study will be considered AE. This includes headaches, gastrointestinal discomfort, and other events captured on the adverse event/compliance sheet that are without significant health risk and/or are potentially unrelated to study. Clinically significant changes in blood pressure or safety monitoring labs will be considered an AE. Specifically, liver function results that exceed two times the upper limit of normal, triglycerides greater than 400 mg/dl, and/or hypotension, with a blood pressure <90mmHg in adults or <the 5th percentile for age in children after taurine supplementation, will

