be considered an adverse event in the setting of normal subject values prior to taurine supplementation. Any intercurrent illness or injury that represents an exacerbation of pre-existing condition (e.g., increase frequency or severity) will also be considered an AE. In such cases it will be preferred to record the diagnosis as the AE rather than a series of terms relating to the diagnosis (e.g., worsening of asthma). An adverse drug reaction will be all noxious and unintended responses to taurine product. This means that a causal relationship between taurine and an AE is at least a reasonable possibility (i.e., the relationship cannot be ruled out).

The PI and one of the co-investigating MDs will determine the severity of the event and if the SAE or AE is related to the protocol using the categories noted below. Review of their determination will be sought from the Safety Officers. In the case of deferring opinions, higher grade of severity the more related rating will be accepted

Grade	Description
Mild	No limitation of usual activities
Moderate	Some limitation of usual activities
Severe	Inability to carry out activities

Not Related	The adverse finding was present prior to exposure to the investigational product, having the same or milder intensity OR The finding is considered likely to be related to an etiology other than the investigational product, that is, there is no evidence or arguments to suggest a causal relationship to the investigational product.
Possibly related	Exposure to investigational product and onset of the finding are reasonably related in time AND The adverse finding could be reasonably be explained by factors or causes other than exposure to investigational product.
Probably related	Exposure to investigational product and onset of the finding are reasonably related in time AND The adverse finding is more likely explained by exposure to investigational product than by other factors or causes.

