Pregnancy testing will be done on day 1, one day prior to the administration of taurine and reviewed by 5:00 PM that day. Positive test results will exclude the individual from participation in the study. A physical examination (to include blood pressure) and the Adverse Event Sheet Questionnaire will be completed on day 1 and just prior to taurine administration respectively. They will be repeated after administration of the last taurine dose. This data will be reviewed within 5 working days after the subject has completed the study protocol. Liver function study results that exceed two times the upper limit, triglycerides results that are greater than 400 mg/dl, and/or hypotension (blood pressure <90mmHg in adults or < the 5th percentile for age in children) as well as any clinically significant alteration in safety monitoring laboratory studies (as assessed by the co-investigating MD) that is present in two or more subjects in the setting of normal subject values before taurine supplementation will be reported to the co-investigators, FDA, COMIRB, CTRC, and Safety Officers within 5 working days of knowledge of this data. The protocol will be temporarily suspended pending review of collected data and recommendation about study continuance by Safety Officers, FDA, COMIRB and CTRC.

All unanticipated problems and unanticipated events will also be discussed with one of the co-investigating MDs within five working days of knowledge of the problem or event. Any identified trend in AEs will also be discussed within five working days of knowledge of the trend with one of the co-investigator MDs.

Compiled data will be examined for safety after 2, 4, and 8 subjects have completed the protocol and at the end of the study by the PI, co investigators and data Safety Officers. The PI, co-investigators and the data Safety Officers board will be looking for repeat adverse events (AEs) or trends in AEs.

SAEs will be reported to the study project manager, the PI or one of the lead site co-investigator MDs, FDA, COMIRB, local IRB as per their requirement, and the CTRC within five working days of knowledge of the event. In addition, the data Safety Officers and PI and co-investigators will convene within one week of reporting of a SAE.

C. Describe both subject discontinuation criteria and protocol stopping criteria:

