With respect to the FMD studies, if an adult systolic blood pressure is < 105 mmHg or a child's blood pressure is < 10th percentile for age, nitroglycerin will not be administered. The subject will otherwise be maintained in the study.

With respect to the study in general, subject discontinuation criteria are as follows.

- Positive pregnancy test
- Any SAE that is possibly related to the study protocol.

Protocol stopping criteria are listed below. Such events will result in the study being temporarily suspended pending review of collected data and recommendation about study continuance by Safety Officers, FDA, COMIRB and CTRC.

- Any SAE that is possibly related to the study protocol.
- Liver function study results that exceed two times the upper limit, if triglycerides are greater than 400 mg/dl, and/or if hypotension (blood pressure <90mmHg in adults or < the 5th percentile for age in children) is present in two or more subjects in the setting of normal subject values before taurine supplementation.
- Any clinically significant alteration in safety monitoring laboratory studies, as assessed by the co-investigating MD and/or the Safety Officers that is present in two or more subjects in the setting of normal subject values before taurine supplementation.

Currently there is no funding source outside of the university, thus we do not expect an outside agent to have authority to suspend this trial, other than general regulatory authorities of the institution and the FDA in its general capacity to oversee drugs and food supplements. Actions that result in suspension or termination of the protocol, whether by COMIRB or some other entity, will be reported to the Pediatric General Clinical Research Center and the IRB verbally within 24 hours and via written documentation within 2 working days.

D. Plans for assuring data accuracy and protocol compliance:

The PI will conduct protocol compliance checks. Accuracy of the laboratory data related to safety is assured via use of Clinical Laboratory Improvement Amendments (CLIA) certified laboratory.

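### The suspension triggers short of an SAE appear to count only subjects with undefined normal values before taurine, so worsening from an eligible but off-range baseline may not oblige suspension

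*Combined protocol and SAP*

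**What the plan says.** **Entry.** Exclusion criterion 10 (Section 5) reads "Individuals with a triglyceride level above 300 mg/dl will be excluded from the study", and adds "Historic triglyceride levels (within 5 years of the date of consent) can be used to assess eligibility". Section 8.A has the level reviewed before dosing: "Those with levels greater than 300 mg/dl will be excluded from the study". The exclusion list has no liver-test limit.

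**Adverse events.** Section 8.B names "liver function results that exceed two times the upper limit of normal, triglycerides greater than 400 mg/dl" and hypotension. These are to "be considered an adverse event in the setting of normal subject values prior to taurine supplementation".

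**Suspension.** Section 8.C lists three triggers: a possibly related SAE; the named thresholds for liver tests, triglycerides and blood pressure; and a catch-all for safety laboratory changes judged clinically significant. The second and third each end with a condition that the finding "is present in two or more subjects in the setting of normal subject values before taurine supplementation". The reporting-flow summary in Section 8.B gives the same rule in one sentence, ending with "any clinically significant alteration in safety monitoring laboratory studies (as assessed by the co-investigating MD) that is present in two or more subjects" and the same baseline condition.

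The documents give no definition of normal and no reference range for triglycerides.

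**The concern.** The plan admits subjects whom its own suspension rule may then leave out of the count. Criterion 10 sets the 300 mg/dl limit because a triglyceride rise (as well as a fall) has been reported with taurine. If a subject must start within a laboratory range to count, the eligible subjects nearest to 400 mg/dl are the ones left out. The same holds for a subject who enters with a slightly raised liver test that then climbs.

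A triglyceride or liver-test rise alone does not meet the SAE definition in Section 8.B. The laboratory triggers are therefore the only rules that oblige a pause and outside review for such a change before more subjects are dosed. The study opens to children from age 8 once four adults have completed it.

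**Working it through.** The plan states no operating characteristic for the suspension rule, so there is no figure to reproduce. The check is to read the triggers against the entry criteria and then apply the rule.

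**1. Where the baseline condition attaches.**

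| Place | Triglycerides > 400 mg/dl | Catch-all laboratory change |
|---|---|---|
| 8.B, AE definition | Attaches clearly, together with liver tests and hypotension | Not conditioned: clinically significant laboratory changes are AEs regardless |
| 8.B, reporting-flow summary | Probably attaches; could belong to the catch-all only | Attaches |
| 8.C, stopping criteria | Probably attaches; could belong to hypotension only | Attaches |

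The joint reading is the most natural one. The AE definition applies the condition to all three measures. On the narrow reading, one triglyceride value above 400 mg/dl from an abnormal baseline would suspend the study without meeting the numeric AE definition.

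**2. What normal could mean.** (a) A laboratory or clinical range: one phrase covers liver tests, triglycerides and blood pressure, and the AE sentence uses the upper limit of normal in its usual laboratory sense. (b) At or below 300 mg/dl: criterion 10 is headed Hypertriglyceridemia, and the screening script wants levels that are not high at study start.

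**3. The rule applied.** Count = number of subjects with pre-taurine value ≤ L and post-taurine value > 400; suspend if the count is at least 2. L is the upper end of normal, which the documents do not give. For two subjects going from 220 to 450 mg/dl (450/220 = 2.05-fold):

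- L = 150, 175, 200 or 219: count 0, no obligatory suspension.
- L = 220, 250 or 300: count 2, suspension.

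**4. Distance to the threshold.** From the entry limit, 400/300 = 1.33, a 33% rise. If L is 150 (assumption; range 130 to 200), a countable subject needs at least 400/150 = 2.67-fold (400/130 = 3.08 to 400/200 = 2.00).

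**5. Illustration only, on assumed inputs.** Usual triglycerides log-normal, median 110 to 140 mg/dl, between-subject log-SD 0.4 to 0.5, within-subject log-SD 0.2 to 0.3. There are 16 exposed subjects (the planned maximum), with screening and Day 2 values both ≤ 300. Ranges are minimum to maximum over eight settings, 40,000 simulated trials each.

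| Average rise | Two or more newly > 400 | Of those, trigger silent, L = 150 | L = 200 | L = 300 |
|---|---|---|---|---|
| 25% | 0.1–7% | 97–100% | 77–98% | 0% |
| 50% | 2–28% | 93–99.9% | 66–92% | 0% |
| 100% | 34–82% | 76–97% | 35–65% | 0% |

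On these assumptions 23–40% of eligible subjects have a Day 2 value above 150 mg/dl. The event is uncommon unless the rise is large. When it occurs, the trigger usually misses it at L = 150 and never at L = 300.

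**6. The catch-all and liver tests.** No numbers are needed. A subject whose liver test is slightly above range before taurine is eligible. On the joint reading that subject is outside the named liver-test trigger, and the catch-all does not help because it carries the same condition.

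**The case against.** The triglyceride gap needs two disputed readings to hold together: that the condition attaches to triglycerides, and that normal ends below 300 mg/dl. In Section 8.C the triglyceride clause is complete by itself and the condition follows hypotension; in the Section 8.B summary it directly follows the catch-all. The protocol's own usage also gives some support to 300 mg/dl as the dividing line, and any lower limit is an outside figure. This stands, and it makes the triglyceride example conditional.

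A reader might infer that such rises would go unreported or unreviewed. The documents do not support that. Clinically significant laboratory changes are AEs without a baseline condition (8.B). Abnormal safety results go to the co-investigator physicians within five working days, and information that changes risk goes to the Safety Officers, FDA, COMIRB and CTRC within five days (8.B). Compiled data are reviewed after 2, 4, 7 or 8, and 12 subjects (8.A and 8.B), and voluntary suspension remains possible. What these routes lack is obligation: they rest on judgement.

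The consequence is limited. Criterion 10 states that "acute health care risk is generally seen in the setting of triglycerides > 1000 mg/dl", the safety review in Section 3 found no consistent pattern, and nothing in the documents suggests that taurine doubles triglycerides. The post-treatment panel falls on Day 6, at the end of dosing, so suspension protects only later subjects. A normal-baseline condition is also a defensible way to avoid stopping for pre-existing dyslipidaemia, but it should then be defined.

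**Conclusion.** The point holds as a minor weakness in the wording of the suspension rule. For triglycerides it is conditional: the gap covers eligible baselines between the upper end of normal and 300 mg/dl. It vanishes if normal means 300 mg/dl or less and the pre-dose value is held to that limit, or if the condition does not attach to triglycerides. For the catch-all trigger no choice of attachment is needed; the condition is there on any reading, and only the ordinary clinical sense of normal is assumed.

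A reader might go further and conclude that the rule certainly ignores high-triglyceride subjects, or that the study has no working safety system. Neither follows: the first depends on unsettled readings, and the second overlooks the reporting and review routes. The simulated percentages rest wholly on assumed inputs and show direction only.

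**What to change.** Change the wording in three places: the AE definition and the reporting-flow summary in Section 8.B, and the stopping criteria in Section 8.C.

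- **Triglycerides.** State that a pre-taurine value of 300 mg/dl or less counts as normal. Alternatively, count any exposed subject whose Day 6 value exceeds 400 mg/dl and whose Day 2 pre-dose value was lower and not above 400. The two versions coincide if the 300 mg/dl limit is applied to the Day 2 value; the second also works where eligibility rested on an older value.
- **Catch-all trigger.** Use *clinically significant worsening from the subject's own pre-taurine value*.
- **Grammar.** Reword both suspension passages so that the two-subject count clearly applies to all listed measures.

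No new sample, visit or staff is needed: the schedule in Section 5.H already has the metabolic and lipid panels on Day 2 (8 AM) and Day 6. The downside is a slightly higher chance of a temporary suspension, and under the second triglyceride version a small rise across 400, such as 395 to 405, would count. On the illustrative assumptions with no taurine effect, that two-subject trigger suspends in 0–0.7% of trials (0–1.3% if only a historic value is held to 300). Reading Section 8.C as a single-subject trigger would do so in 0.6–12%, so settling the grammar also avoids needless stops.

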
Supplementary materials:

1. Intake Sheet

Oxidative Stress Markers in Inherited Homocystinuria and the Impact of Taurine Intake Sheet

Subject Name: _____ Date: _____

Characteristic	Comment
Sex	
Age	
BMI	
Salicylate intake over last two weeks	
Vitamin intake over last two weeks	
Supplement intake over last two weeks (taurine)	
Viagra intake over last two week/possible use over next 6 days	
Smoking habits	
Hypertension	
Diabetes	

Other chronic disease Infection Hormone replacement use Pregnancy Physical activity Diet prescription/compliance Medications/compliance (list all medications and dosing_)	
---	--

Reviewed by PI or co-investigator on: _____
 Proceed for nitroglycerin induced FMD YES/NO*
 Proceed for platelet studies YES/NO*
 *circle appropriate

			Comments (to include any limitations of activity)
System	Yes	No	
General/Constitutional			
general state of health			
sense of well being			
fever			
other			
Skin			
rash			
moisture/dryness			
other			
HEENT			
headaches			
vision			
hearing			
other			
Cardiovascular			
palpitations			
syncope			
other			
Respiratory			
difficulty breathing			
wheezing			
cough			
other			
Gastrointestinal			
appetite			
abdominal pain			
heartburn			
diarrhea			

	nausea			
	other			
Musculoskeletal				
	pain			
	cramps			
	other			
Genitourinary				
	dysuria			
	other			
Neurologic/Psychiatric				
	seizures			
	muscular coordination			
	emotional mood			
	other			
Allergic/Immunologic				
	reactions to drugs/foods			
	other			

II. Adverse Event Sheet:

Oxidative Stress Markers in Inherited Homocystinuria and the Impact of Taurine
 Adverse Event/Compliance Sheet

Subject Name: _____ Date: _____ Taurine intake:

System	Yes	No	Comments
General/Constitutional			
general state of health			
sense of well being			
Fever			
Other			
Skin			
Rash			
moisture/dryness			
Other			
HEENT			
Headaches			
Vision			
Hearing			
Other			

Cardiovascular				
	Palpitations			
	Syncope			
	Other			
Respiratory				
	difficulty breathing			
	Wheezing			
	Cough			
	Other			
Gastrointestinal				
	Appetite			
	abdominal pain			
	Heartburn			
	Diarrhea			
	Nausea			
	Other			
Musculoskeletal				
	Pain			
	Cramps			
	Other			
Genitourinary				
	Dysuria			
	Other			
Neurologic/Psychiatric				
	Seizures			
	muscular coordination			
	emotional mood			
	Other			
Allergic/Immunologic				
	reactions to drugs/foods			
	Other			

III. Reportable event sheet

Oxidative Stress Markers in Inherited Homocystinuria and the Impact of Taurine
Reportable Event Sheet

	EVENT	Date of Knowledge of Event	Date Reported to COMIRB	Comments
	Unforeseen harmful/unfavorable event, felt to possibly be related to study			
	injury			
	psychological event			
	other			

Unforeseen harmful/unfavorable event, felt to be unrelated to study			
injury			
psychological event			
other			
Unforeseen development that increases likelihood of harm			
midterm review			
new safety data on taurine supplementation			
other			
Problem involving data			
data collection			
data storage			
data privacy			
data confidentiality			
Change in subjects status			
incarceration of subject			
pregnancy of subject			
other			
Change in protocol for subject safety done prior to COMIRB review			
apparent immediate hazard			
Complaint of participant that can't be resolved or suggest risk			
complaint			
Unintentional protocol violation that harmed or may cause harm			
violation			
Noncompliance by the PI or research team			
noncompliant activity			
Other			
other			

IV. Advertisement for subject recruitment

Advertisement for subject recruitment:

You are invited to participate in a study investigating homocystinuria. The study is being conducted by (Site Specific Providers) at (Site Location). The study investigates why individuals with homocystinuria have health problems and if a new investigative treatment with taurine is beneficial. The study will not provide direct benefit to the participant but will provide generalizable information on homocystinuria.

To be eligible to participate in the study individuals must be between the ages of 8 to 50 year and have a diagnosis of homocystinuria due to cystathionine beta-synthase deficiency that is not fully responsive to therapy with total homocysteine (tHcy) levels greater than 50 $\mu\text{mol/L}$. Individuals cannot participate if they are (1) pregnant, (2) have hypertriglyceridemia, (3) have another significant illness, and/or (4) are being treated with Vitamin C, taurine supplementation, and/or high dose antioxidant supplementation and cannot discontinue this.. Participants who have a cold, the flu or other short term illness will be asked to delay participation until they are recovered.

